#### B.4.7. Sample Size & Power Analysis

We expect an approximate drop-out rate of 25% based on our current, more burdensome protocol within a sample of 18-40 year-old females. Therefore, we will enroll a total of 125 female and 125 male participants to ensure we have 100 per sex group to complete the 4 week follow-up for the primary outcome. Participants will be randomized 1:1 to PRO or placebo, separately by sex group, as described above. In our earlier work ([name] et al, 2008), the luteal quit group had a prevalence of 66% relapse at 30 days; this estimates the placebo group relapse rate for our proposed study. Based on a two-tailed Pearson chi-square test with alpha=0.025 for each sex group, a sample size of 100 completers per sex group will have 80% power to detect an odds ratio of 3.5 or higher for comparing smoking relapse prevalence in the placebo group to smoking relapse prevalence in the PRO group. We observed an odds ratio of 3.2 for follicular quit group relapse compared to luteal quit group relapse ([name] et al, 2008). Since our PRO group will receive substantially more progesterone than the typical natural female cycle, it is reasonable to expect a slightly larger odds ratio for PRO compared to placebo. Since the difference in progesterone levels between the male PRO group and the male PBO group will be larger than the difference between the female PRO group and the female PBO group (see Figure 5), we expect a larger odds ratio (hence higher power) for the male treatment comparison.

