#### B.4.1. Study Design

This double-blind, clinical trial (Figure 4) will prescreen an estimated 600 potential subjects, consent and evaluate approximately 300 potential subjects and ultimately enroll 250 subjects to ensure 200 subjects provide a primary relapse outcome measure at four weeks after quit date. Subjects will be stratified by sex then randomized to one of two groups (n=100 per group / 50% female): Progesterone (PRO) or Placebo (PBO). Telephone screening and visit invitation (20 minutes) leads to the consent process and in-person screening including medical-psychiatric evaluation for inclusion/exclusion (two visits, two hours each), then randomization and medication induction (seven days), stable medication (70 days) with medication reduction and final evaluation for secondary outcomes (over the last seven days). These procedures will be conducted as described below.

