#### B.4.2. Setting, Recruitment, Subjects

Setting: This project will be conducted at the Delaware Clinical Research Unit (DCRU). The DCRU has both inpatient and outpatient resources for the spectrum of biomedical research including special capabilities that were developed for study of substance use disorders. The Clinical and Translational Sciences Institute (CTSI), runs the DCRU and functions parallel and support the activities of the NIH funded CTSA, which it predated.

The DCRU includes: reception area, examination rooms, meeting rooms, clinical interview rooms, testing rooms for computer based performance tasks, a wet lab for handling bloods and other specimens, freezers (to -80°C), all essential staff offices, each with multiple telephone and computer lines through the University of Minnesota servers, a locked limited access protocol, equipment and medication rooms, as well as secure cabinets for study files and essential supply and support areas and services.

**Recruitment:** To meet recruitment goals, we aim to enroll a total of 250 subjects (~6 subjects/month) to ensure a final sample size of 100 females and 100 males. Our primary recruitment method will be advertising in the mainstream media. While this type of recruitment can be challenging, our team has been successful with this form of recruitment. For example, our current study recruiting females between the ages of 18-40 has had success with Facebook advertising. Specifically, over the past seven months we have advertised on Facebook resulting in 6,483 clicks to our website, an estimated 180 phone calls to our clinic and an enrollment of 29 subjects (~4 subjects/month). We regularly use television, radio, mailings, and other internet sources to identify study subjects with similar success. Using all of these methods, we have successfully enrolled ~8 subjects/month over the past year in our two ongoing tobacco use research studies.

**Subjects and Eligibility:** Females 18-50 years of age with regular menstrual cycles and males, 18-60 years of age, (n=300; 50% females) will be enrolled who are current smokers and are motivated to quit smoking.

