Study Adherence: To encourage compliance the following will occur: (1) at the Baseline Visit, subjects will be given a schedule of all remaining appointments; (2) at each visit the subjects will be given an appointment reminder card for the next visit; (3) reminder calls, texts and/or emails (per subject's preference) will be placed or sent the day before each visit; (4) subjects will be routinely reminded that regardless of their smoking status their data are valuable and important; and (5) regardless of smoking status, subjects will be compensated at each visit (described in the following). If a subject misses a visit, study staff will try to reach him/her by phone that day to reschedule for one to three days later. If that does not work, staff will contact the subject's designated 'contact person' (i.e., someone who does not live with the subject but knows how to get in touch). If a subject does not attend any visits after the screening visits, he/she will be labeled as a "drop" and replaced. If the subject discontinues from the study after randomization but before the final follow-up visit, he/she will be labeled an "*incomplete*" but not replaced. If a subject does not quit on their assigned quit date or relapses later, she/he will be encouraged to stay in the study and make another quit attempt; such that we will follow them for three months regardless of smoking status. Subjects who complete the four week follow-up period after quit date, regardless of smoking status, will be labeled a "*completer*" for the primary outcome and not replaced. Our sample size goal to sufficiently power the primary outcome is for 200 completers.

[figure not shown]

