#### B.4.8. Statistical Analysis

Randomization scheme: Our power calculation for the primary outcome specifies 100 males and 100 females. Since we expect approximately 25% drop-out before determination of the primary endpoint, we will over-enroll, approximately 125 of each sex. Thus we will build randomization tables for up to 150 male and 150 female potential enrollees. Each sex group will be randomized 1:1 to PRO vs. PBO. Since enrollment and randomization will occur over several years, we will employ a randomly permuted blocks allocation, rather than a simple random allocation, stratified by sex. This will reduce the possibility of a chance imbalance in treatment assignments, ensuring that we have treatment balance maintained within sex group consistently across the enrollment period. Block sizes of 4 and 6 will be used in a 1:1 ratio.

Primary outcome analyses: This addresses Hypothesis 1. Our primary outcome is the binary indicator of relapsed yes/no at the week 4 visit. An unadjusted assessment of the treatment effect will come from a logistic regression of this binary outcome on randomized treatment assignment, separately by sex. The sex-specific treatment effect will be considered statistically significant if the p-value is <0.025. All persons randomized and with a measured primary outcome at the week 4 visit will be included in this analysis, regardless of whether or not they ever took any of their assigned treatment (intent-to-treat analysis); persons with missed visits are discussed below. While we expect baseline covariates to be balanced across treatment groups due to the randomization, an adjusted assessment of the treatment effect will then be carried out by a logistic regression including the randomized treatment assignment and pre-specified adjusting covariates such as age, baseline progesterone, estradiol, baseline impulsivity measures, etc. This pre-specified list will be determined by the study team during the finalization of the protocol, prior to the first study enrollment. We expect these analyses to be somewhat conservative, since they do not explicitly account for the randomized permuted blocking (Matts and Lachin, 1988). An analysis that accounts for the blocking (such as a stratified Mantel-Haenzel test) cannot be generalized to include the adjustment for impulsivity measures, for example, which are a focus of this proposal.

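### At the stated drop-out of about 25% before week 4, enrolling 125 per sex yields about 94 completers per sex, not 100; an expected 100 needs 134

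*Combined protocol and SAP*

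**What the plan says.** Section B.4.7 takes an approximate drop-out of 25% from the team's ongoing, more burdensome study in women aged 18 to 40. It then states that "we will enroll a total of 125 female and 125 male participants to ensure we have 100 per sex group" completing the 4-week follow-up. The DSMP section on power and sample size repeats this. Section B.4.8 (randomization scheme) fixes the timing of the loss: "Since we expect approximately 25% drop-out before determination of the primary endpoint, we will over-enroll, approximately 125 of each sex". It adds: "Thus we will build randomization tables for up to 150 male and 150 female potential enrollees".

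The same ratio appears in section B.4.1, which will "ultimately enroll 250 subjects to ensure 200 subjects provide a primary relapse outcome measure", and in section B.4.2: "we aim to enroll a total of 250 subjects (~6 subjects/month) to ensure a final sample size of 100 females and 100 males". The Study Adherence paragraph of B.4.3 sets the target: "Our sample size goal to sufficiently power the primary outcome is for 200 completers". It replaces subjects who attend no visit after screening. Those who discontinue after randomization are labelled incomplete and are not replaced.

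The power claim in B.4.7 rests on 100 completers per sex: 80% power for an odds ratio of 3.5, placebo relapse 66%, two-sided Pearson chi-square test at 0.025 within each sex.

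**The concern.** The enrolment figure is presented as a consequence of the drop-out figure, and it is not one. A 25% loss applied to 125 leaves fewer than 100. The stated 125 equals 100 × 1.25, which suggests that the target was multiplied by one plus the drop-out rate instead of divided by one minus it. The plan does not show its calculation, so this is only a likely explanation.

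What is at stake is the 200-completer goal and the 80% power that depends on it. The design has little slack: each sex is tested separately at 0.025, and the only empirical odds ratio cited in B.4.7 is 3.2, already below the 3.5 used for power.

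**Working it through.** **Inputs**
- Drop-out 25% (B.4.7), before the primary endpoint (B.4.8).
- Enrolment 125 per sex; target 100 completers per sex (B.4.7).
- Placebo relapse 66%, odds ratio 3.5, two-sided alpha 0.025 per sex, 1:1 allocation (B.4.7).

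**1. The plan's power statement reproduces.** Placebo odds are 0.66 / 0.34 = 1.941. Dividing by 3.5 gives 0.5546, so the PRO relapse rate is 0.5546 / 1.5546 = 0.3568, the difference is 0.3032 and the mean rate is 0.5084. By the pooled-variance normal approximation with n per arm,

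power = Φ{[0.3032 − 2.2414 × √(2 × 0.5084 × 0.4916 / n)] / √[(0.66 × 0.34 + 0.3568 × 0.6432) / n]}.

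At n = 50: Φ[(0.3032 − 2.2414 × 0.1000) / 0.0953] = 79.7%, against the stated 80%.

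**2. The enrolment statement does not reproduce.**
- Expected completers from 125: 125 × (1 − 0.25) = 93.75 per sex, or 187.5 in total.
- Enrolment for 100 completers: 100 / (1 − 0.25) = 133.3, rounded up to 134 per sex, or 268 in total.
- Drop-out at which 125 is right: 1 − 100/125 = 20%.

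**3. Power with 93.75 completers (46.875 per arm).** Φ[(0.3032 − 2.2414 × 0.1033) / 0.0984] = 76.7%. The odds ratio detectable with 80% power rises from 3.52 to 3.67.

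**4. Chance of at least 100 completers in one sex**, with completers binomial at retention 0.75:

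| Enrolled per sex | Expected completers | P(at least 100) |
|---|---|---|
| 125 | 93.75 | 11.6% |
| 134 | 100.5 | 58.5% |
| 145 | 108.75 | 95.9% |
| 150 | 112.5 | 99.1% |

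For both sexes to reach 100 from 125 each: 0.116² ≈ 1.3%.

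**5. Exact check.** Power of the uncorrected Pearson test, averaged over random completer counts in each arm at retention 0.75, is 76.9% with 125 enrolled (63 + 62) and 80.1% with 134 (67 + 67). At fixed counts exact power is not monotone, because the test is discrete: 78.3% at 50 per arm, 79.3% at 47, 77.6% at 46. The 3-point loss is therefore an average over likely completer counts.

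**6. Sensitivity to the drop-out rate** (125 enrolled, normal approximation):

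| Drop-out | Completers per sex | Power at odds ratio 3.5 |
|---|---|---|
| 20% | 100 | 79.7% |
| 25% | 93.75 | 76.7% |
| 30% | 87.5 | 73.4% |

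**The case against.** Five points can be made for the plan.

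- **The 25% may be cautious.** It is called approximate and comes from a heavier protocol. At 20% the 125 is exact, and the chance of reaching 100 becomes 55%. This softens the point, but the plan says it expects 25%, states 20% nowhere, and the true rate could equally be higher.
- **Some losses are replaced.** Subjects with no visit after screening are replaced, and the document uses the word enrolment loosely. However, randomization takes place at the later Baseline Visit, and B.4.8 ties the over-enrolment to the randomization tables. Losses after randomization are not replaced.
- **The tables run to 150 per sex and the goal is set in completers.** The capacity is real and would give about a 99% chance of 100 completers per sex. What is missing is a rule linking continued enrolment to the completer count. Apart from one mention of n = 300 in B.4.2, which conflicts with the 250 given in the same section, the stated enrolment targets are 125 per sex or 250 in total.
- **Week 5 recall could recover outcomes.** B.4.8 uses recalled outcomes in one of three versions of the primary analysis. The power statement is for completers, so recall does not repair it.
- **The effect is small.** This stands. The average loss is about 3 percentage points, and even 134 per sex gives an expected 100 rather than a guarantee.

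**Conclusion.** The enrolment figure is wrong as written. On the plan's own inputs, 125 per sex is expected to give about 94 week 4 completers: about 6 short per sex and about 12 in total. Average power at an odds ratio of 3.5 is about 77% per sex, not 80%, and the detectable odds ratio is about 3.7, not 3.5.

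The completer counts need only the stated 25%. The power figures also use the stated 66% placebo relapse and equal retention in the two arms. The probabilities of reaching 100 further assume independent drop-out. The shortfall does not undermine the trial, but the promise of 100 completers per sex cannot stand next to a 25% drop-out.

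**What to change.** Choose one of two routes and state it consistently.

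**Restate.** Say that 125 enrolled per sex is expected to give about 94 week 4 completers per sex, with approximately 77% power at an odds ratio of 3.5 (averaged over likely completer counts), or 80% at about 3.7. This is a text correction with a slightly less favourable power figure and no extra subjects. It changes B.4.1, B.4.7, B.4.8, the 200-completer goal in B.4.3, and the DSMP power section.

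**Enrol more.** Keep the goal of 100 completers per sex, state that enrolment continues to about 134 per sex, and describe the 100 as expected. If near-certainty is wanted, about 145 per sex gives a 96% chance in each sex. Both fit the 150-per-sex tables. Going to 134 adds 268 − 250 = 18 subjects, or 3 months at the stated 6 or so per month. In all, 268 / 6 = 44.7 months, against 45 months (15 quarters) of recruitment in Table 2 of the protocol and 54 months (18 quarters) in the DSMP timeline. The 145 option needs 290 / 6 = 48.3 months, which fits only the DSMP timeline. The two timelines should be reconciled.

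**In either case, align the totals.** Section A randomly assigns 200. B.4.1 consents about 300 to enrol 250. B.4.2 enrols both 250 and 300. The DSMP recruitment text and enrolment table give 250 enrolled, while its eligibility section says 250 are consented. The final-sample figures of 100 per sex in B.4.2 and the DSMP should follow whichever route is chosen.

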#### B.4.8. Statistical Analysis

Randomization scheme: Our power calculation for the primary outcome specifies 100 males and 100 females. Since we expect approximately 25% drop-out before determination of the primary endpoint, we will over-enroll, approximately 125 of each sex. Thus we will build randomization tables for up to 150 male and 150 female potential enrollees. Each sex group will be randomized 1:1 to PRO vs. PBO. Since enrollment and randomization will occur over several years, we will employ a randomly permuted blocks allocation, rather than a simple random allocation, stratified by sex. This will reduce the possibility of a chance imbalance in treatment assignments, ensuring that we have treatment balance maintained within sex group consistently across the enrollment period. Block sizes of 4 and 6 will be used in a 1:1 ratio.

Primary outcome analyses: This addresses Hypothesis 1. Our primary outcome is the binary indicator of relapsed yes/no at the week 4 visit. An unadjusted assessment of the treatment effect will come from a logistic regression of this binary outcome on randomized treatment assignment, separately by sex. The sex-specific treatment effect will be considered statistically significant if the p-value is <0.025. All persons randomized and with a measured primary outcome at the week 4 visit will be included in this analysis, regardless of whether or not they ever took any of their assigned treatment (intent-to-treat analysis); persons with missed visits are discussed below. While we expect baseline covariates to be balanced across treatment groups due to the randomization, an adjusted assessment of the treatment effect will then be carried out by a logistic regression including the randomized treatment assignment and pre-specified adjusting covariates such as age, baseline progesterone, estradiol, baseline impulsivity measures, etc. This pre-specified list will be determined by the study team during the finalization of the protocol, prior to the first study enrollment. We expect these analyses to be somewhat conservative, since they do not explicitly account for the randomized permuted blocking (Matts and Lachin, 1988). An analysis that accounts for the blocking (such as a stratified Mantel-Haenzel test) cannot be generalized to include the adjustment for impulsivity measures, for example, which are a focus of this proposal.

Safety analyses: Adverse events will be quantified separately by sex and treatment groups and compared across treatment groups with Fisher's exact test (for binary events) or with chi-square test (for counts of events or event rates).

Secondary outcome analyses: These address Hypothesis 2. Our secondary outcomes include the binary indicator of relapsed yes/no at the week 12 visit, and days to relapse, as described above. The binary outcome will be analyzed as described for the primary outcome. Days to relapse will be analyzed using Kaplan-Meier

curves with a log-rank test comparing treatments (unadjusted) and Cox proportional hazards analysis (adjusted for other characteristics), both of which allow for loss-to-follow up via right censoring (Therneau and Grambsch, 2000), separately for the CA and PA definitions. Adjusting variables will be selected as described for the primary outcome. The proportional hazards assumption on the treatment effect will be examined and tested (Lin, Wei, and Ying, 1993; Grambsch and Therneau, 1994).

Other analyses: To address Hypothesis 3, we will pool the male and female data and test for an interaction between sex and treatment assignment in an adjusted Cox regression for the days to relapse outcomes. To address Hypothesis 4, we will test a baseline impulsivity by sex interaction in the logistic regressions for the binary outcomes and in the Cox regressions for the days to relapse outcomes. To address Hypothesis 5, we will test a baseline impulsivity by baseline serum progesterone interaction in the logistic regressions for the binary outcomes and in the Cox regressions for the days to relapse outcomes. While this study was designed to be powered for Hypothesis 1, rather than for these comparisons, these will be used to generate preliminary data and hypotheses for future research on sex differences in addiction treatment and impulsivity.

Handling missing outcomes: For persons who do not attend a week 4 visit, assessment of the primary outcome is not directly possible. During their week 5, study staff will attempt to contact them in order to collect by phone and/or email a self-reported recall of smoking status as of week 4; outcomes collected in this way will be denoted separately in the study database. The primary outcome analysis will be carried out once excluding these persons, once including those for whom we were able to obtain a self-reported recall outcome, and once where we conservatively assume all these persons relapsed as of their week 4 visit. Since 'missing at random' is a strong statistical assumption to make in the primary outcome analysis, we will also carry out descriptive analyses to see whether persons missing their week 4 visit differed in their baseline characteristics or treatment assignment from persons not missing their week 4 visit.

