### **Aim 1: Investigate sex differences in the effect of exogenous PRO compared to placebo on impulsivity and smoking cessation**

Hypothesis 1: For both males and females, a lower proportion of subjects randomized to PRO will relapse by 4 weeks after quit date compared to those randomized to PBO.

Hypothesis 2: For both males and females, subjects randomized to PRO will have more days to relapse compared to those randomized to PBO.

Hypothesis 3: There will be a sex difference in smoking relapse such that females, regardless of randomization assignment, will have fewer days to relapse compared to males.

Hypothesis 4: Impulsivity will be a stronger relapse predictor in females than males.

Hypothesis 5: Among those with higher levels of serum PRO the influence of impulsivity on smoking relapse will be dampened.

Given that less than three percent of those who attempt to quit smoking remain abstinent six months later (Benowitz, 2009), there is an urgent need to gain a better understanding of the dynamic process involved in smoking cessation. This project will provide new knowledge regarding the possible protective role of progesterone against smoking relapse in males and females.

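### The fixed 0.025 threshold per sex is valid, but a Holm step-down rule would raise per-sex power from 79.7% to 85.5% if the odds ratio is 3.5 in both sexes; it gains almost nothing if only one sex benefits

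*Combined protocol and SAP*

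**What the plan says.** Hypothesis 1 in the Specific Aims covers the two sexes together: "For both males and females, a lower proportion of subjects randomized to PRO will relapse by 4 weeks after quit date", compared with placebo. B.4.8 (Primary outcome analyses) implements it as two unadjusted logistic regressions of Week 4 relapse on randomized arm, one per sex, with the rule "The sex-specific treatment effect will be considered statistically significant if the p-value is <0.025". DSMP section C repeats this. The analysis set in B.4.8 is defined by "All persons randomized and with a measured primary outcome at the week 4 visit will be included in this analysis".

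The sample size section, B.4.7, uses the same level: "Based on a two-tailed Pearson chi-square test with alpha=0.025 for each sex group". It claims 80% power for an odds ratio (OR) of 3.5 with 100 completers per sex, taking placebo relapse as 66%. For context it reports "We observed an odds ratio of 3.2 for follicular quit group relapse compared to luteal quit group relapse", and it adds "we expect a larger odds ratio (hence higher power) for the male treatment comparison". The power section of the DSMP repeats these statements.

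Neither document names a family-wise error level or describes a step-down procedure. Both give power per sex only.

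**The concern.** Two tests at 0.025 each use up a 5% family-wise budget in the simplest way. Under that rule, a sex with a p-value between 0.025 and 0.05 is declared negative even when the other sex is clearly positive. Holm's procedure would declare it positive within the same 5%.

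This affects the trial's primary decision. If PRO works equally well in both sexes at the design OR, about one trial in three would still end with one sex positive and the other negative. In a trial about sex differences, such a split is easily taken for a real one.

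**Working it through.** **Inputs.** From B.4.7: placebo relapse 66%, OR 3.5, two-sided alpha 0.025, Pearson chi-square, 100 completers per sex. From B.4.8: 1:1 allocation within sex, hence 50 per arm, and separate models by sex. The two samples do not overlap, so the two tests are independent. Assumption: the intended family-wise level is 5% (2 × 0.025).

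**Step 1: reproduce the stated power.** Placebo odds are 0.66/0.34 = 1.941. Dividing by 3.5 gives 0.555, a PRO relapse rate of 35.7% and a difference of 0.3032. The pooled standard error is √(2 × 0.5084 × 0.4916/50) = 0.1000; the unpooled one is √((0.66 × 0.34 + 0.3568 × 0.6432)/50) = 0.0953.
- At 0.025: Φ((0.3032 − 2.241 × 0.1000)/0.0953), so *a* = 0.797. The stated 80% reproduces.
- At 0.05: the same with 1.960, so *b* = 0.870.

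**Step 2: formulas.** With F and M for the sexes:
- Holm power for one sex: a + (b − a) × a_other.
- Both significant: fixed a_F × a_M; Holm b_F × b_M − (b_F − a_F)(b_M − a_M).
- At least one significant: 1 − (1 − a_F)(1 − a_M), the same under both rules.

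**Step 3: OR 3.5 in both sexes.**
- Per sex: 0.797 + 0.073 × 0.797 = 0.855.
- Both: 0.797² = 0.635 fixed; 0.870² − 0.073² = 0.751 Holm.
- At least one: 1 − 0.203² = 0.959.
- Exactly one: 0.959 − 0.635 = 0.324 fixed; 0.959 − 0.751 = 0.207 Holm (from unrounded values).

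**Step 4: other scenarios (fixed to Holm).**

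| Scenario | Per sex | Both sexes |
|---|---|---|
| OR 3.2 in both | 72.9% to 79.3% | 53.1% to 65.9% |
| OR 2 in both | 29.0% to 32.0% | 8.4% to 14.4% |
| OR 3.5, 47 per arm (125 × 0.75/2) | 76.8% to 83.0% | 59.0% to 71.3% |
| Female 3.5, male 4 (assumed) | – | 69.8% to 80.3% |
| Female 3.5, male 5 (assumed) | – | 76.1% to 84.9% |
| OR 3.5, other sex null | 79.7% to 79.9% | see step 5 |

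The null case is 0.797 + 0.073 × 0.025 = 0.799.

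**Step 5: cost when PRO works in one sex only.** The null sex is falsely significant with probability 0.025 + 0.025 × a_other, against 0.025 under the fixed rule: 4.5% at OR 3.5, 4.7% at OR 4 and 4.9% at OR 5. A false claim of benefit in both sexes at OR 3.5 goes from 0.797 × 0.025 = 2.0% to 0.870 × 0.05 − 0.073 × 0.025 = 4.2%. With no effect in either sex, family-wise error is 1 − 0.975² = 4.9% under both rules.

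**Step 6: the planned test itself.** Exact binomial enumeration of the logistic (Wald) test, 50 per arm and OR 3.5 in both sexes, gives per-sex power of 78.1% fixed and 86.0% Holm, and both-sex success of 61.0% and 76.8%. The gain therefore does not come from the chi-square approximation. The exact size of the Wald test at nominal 0.05 is 4.7% when relapse is 66% in both arms and 5.7% when it is 50%, so the error rates in step 5 are nominal.

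**The case against.** The plan contains no mistake here. The threshold and the power calculation agree throughout, and keeping 0.025 is a legitimate preference. The trial asks about sex differences. If PRO works in one sex only, Holm adds 0.2 points of power, nearly doubles the null sex's error and makes one sex's verdict depend on the other's. The gain is also modest when effects are small. All of this stands as a cost to be disclosed. It does not make Holm invalid, and B.4.7 itself expects an effect in both sexes.

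The 5% family-wise level is an inference. If the team meant 0.025 as a strict standard for each sex, testing the second sex at 0.05 would breach it. The amendment therefore has to state the level.

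Timing also counts. The sheet headed SCOR P1 and MJ Rules/Changes carries operating rules dated from January 2015 and was last updated in September 2016, so the trial appears to have been running. The statistics core knows the allocation from the Baseline Visit (B.4.3, B.4.6). Relaxing a primary threshold late could cost credibility. Against that, the DSMP plans no interim efficacy analysis and places data analysis at the end of the study.

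A reader might infer from the wording of Hypothesis 1 that the trial's real power is 63.5% and the stated 80% is misleading. The documents do not support this. B.4.8 gives a separate verdict for each sex, and nothing makes significance in both sexes the criterion for success. Per-sex power matches the rule as written.

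**Conclusion.** This is an inexpensive improvement, not an error. Holm rejects whenever the fixed rule does and keeps the same nominal 5% family-wise level. At OR 3.5 in both sexes it adds 5.8 points of power per sex (79.7% to 85.5%) and 11.6 points to the chance of success in both (63.5% to 75.1%). Split results become less frequent but do not disappear (32.4% to 20.7%).

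The conclusion assumes a 5% family-wise target, 50 completers per arm and 66% placebo relapse. The benefit needs an effect in both sexes. The male ORs of 4 and 5 are assumptions, since the plan gives no male figure. It would be too strong to say that Holm costs nothing or that error can never exceed 5%.

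**What to change.** Amend B.4.8 and DSMP section C, with a date, before anyone compares outcomes by arm. State that the family-wise level for Hypothesis 1 is 5%. For the unadjusted Week 4 analysis in the measured-outcome set already defined in B.4.8, replace the threshold with:

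> The smaller of the two sex-specific p-values is tested at 0.025; if significant, the other is tested at 0.05.

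Record the downsides in the same amendment:
- If PRO works in one sex only, the null sex's nominal error rises from 2.5% to about 4.5% at OR 3.5 (4.7–4.9% at assumed ORs of 4–5), and false claims for both sexes rise from 2.0% to 4.2%.
- The two verdicts become linked.
- Simple 97.5% confidence intervals no longer match the rule for the second sex.

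Optionally, add one sentence on both-sex power to B.4.7 and the DSMP power section: 63.5% under the fixed rule and 75.1% under Holm, at OR 3.5 in both sexes.

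If outcomes have already been compared by arm, keep 0.025. The Week 12 binary outcome and the choice among the missing-data versions of the primary analysis are separate matters and are not changed here. The cost is one amendment; no patients, visits or data are added.
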